9.3. Populations for Analyses

For purposes of analysis, the following populations are defined:

| Population | Description |
|----------------------------------|--|
| Enrolled | All participants who sign the informed consent form |
| Randomized | All participants who were randomized into the study |
| Safety | All randomized participants who take at least 1 dose of study intervention. |
| PK | All participants who receive at least 1 dose of study drug and who have at least 1 plasma concentration data value after dosing. |
| Intent-to-treat infected (ITT-i) | All randomized participants with a DENV infection who received at least one dose of the study intervention |
| Per-protocol | All participants who are included in the ITT-I population without protocol violations that affect the antiviral activity assessment. |

9.4. Statistical Analyses

The statistical analysis plan will be finalized prior to interim database lock and it will include a more technical and detailed description of the statistical analyses described in this section. This section is a summary of the planned statistical analyses of the most important endpoints including primary and key secondary endpoints. Exploratory subgroup analysis can be performed for the different drug formulations used in the trial.

9.4.1. General Considerations

Participants will be classified prior to data base lock as being non-DENV infected, primary DENV infected or secondary DENV infected based on all available virological information. The decision whether the participant had a primary or secondary infection will be based on the IgG profile.

An interim analysis will be performed when at least 50 participants with a primary dengue infection reached Day 28 or discontinued earlier. Based on the results of this analysis, the DRC and study team can take the decision to stop the trial for futility.

The primary analysis will be performed when all participants reached Day 28 or discontinued earlier. A one-sided test at the 5% significance level will be used for the hypothesis that JNJ-64281802 is superior to placebo in participants with a primary infection.

The final analysis will be performed when the last visit of the last participant in the study occurred.

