| Blood sample collection for pharmacokinetics (CCI formulation) | | | ● | X | X | ● | | ● | X | X | ● | | ● | ● | ● | X | X | X | X | X | X | X | X |

| Phase | Pre-screening (optional) | Screening/Baseline ^a | Double-blind Treatment ^b | | | | | | | | | | | | | | | Follow-Up ^b | | | Early Exit Visit ^b |
|---|--------------------------|---------------------------------|--|--|--|---|--|---|----------------|----------------|----------------|----------------|---|---|---|----|----|------------------------|---|---|-------------------------------|
| | | | During inpatient stay (or ambulatory visits ^y) | | | | | | | | | | | | Extended stay at inpatient facility (for participants with dengue warning symptoms) | | | During on Site Visits | | | |
| Day | | 0 ^a | 1 ^a | | | 2 | | | 3 ^y | 4 ^y | 5 ^y | 6 ^y | 7 | 8 | 9 | 14 | 21 | 28 | | | |
| Month | | | | | | | | | | | | | | | | | | | | 6 | |
| CCI | | | | | | | | | | | | | | | | | | | | | |
| Blood sample collection for plasma protein binding ^f | | | ● | | | | | | | | | X | | | X | | | | | | |
| Blood sample collection for alpha 1 acid glycoprotein ^f | | | ● | | | | | | | | | X | | | X | | | | | | |
| Antiviral activity Assessments | | | | | | | | | | | | | | | | | | | | | |
| Blood sample collection for viral load determination (DENV RNA, infectious virus and NS1) | | X | | | | X | | ● | | | X | X | X | X | X | X | X | X | X | X | X |
| Immune/Viral sequencing Assessments | | | | | | | | | | | | | | | | | | | | | |
| Blood sample collection for humoral immunity (IgG, IgM and nAb) | | X | | | | | | ● | | | | X | X | X | X | X | X | X | X | X | X |

[figure not shown]

| Phase | Pre-screening (optional) | Screening/Baseline ^a | Double-blind Treatment ^b | | | | | | | | | | | | | | | Follow-Up ^b | | | Early Exit Visit ^b |
|---|--------------------------|---------------------------------|--|--|---|---|---|--|----------------|----------------|----------------|----------------|---|---|---|----|----|------------------------|----------------|---|-------------------------------|
| | | | During inpatient stay (or ambulatory visits ^y) | | | | | | | | | | | | Extended stay at inpatient facility (for participants with dengue warning symptoms) | | | During on Site Visits | | | |
| Day | | 0 ^a | 1 ^a | | | 2 | | | 3 ^y | 4 ^y | 5 ^y | 6 ^y | 7 | 8 | 9 | 14 | 21 | 28 | | | |
| Month | | | | | | | | | | | | | | | | | | | | 6 | |
| CCI | | | | | | | | | | | | | | | | | | | | | |

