| 
 Investigate the antiviral activity of JN-64281802 versus placebo in terms of reduction of DENV RNA in secondary DENV infections and in all DENV infections | 
 Virologic endpoints derived from the DENV RNA, viral load, including 
 Area under the log₁₀-transformed DENV RNA viral load curve from baseline until Day 5, in secondary DENV infection Occurrence of detectable DENV RNA at each time point in secondary DENV infection Time to undetectable DENV RNA in secondary DENV infection |

| Objectives | Endpoints |
|---|--|
| 
 Investigate the antiviral activity of JNJ-64281802 versus placebo based on viremia in secondary DENV infections and in all DENV infections | 
 Virologic endpoints derived from viremia, including 
 Area under the log₁₀-transformed viremia curve from baseline until Day 5 in secondary DENV infection Occurrence of detectable viremia at each timepoint in secondary DENV infection Time to undetectable viremia in secondary DENV infection |
| 
 Investigate the effect of JNJ-64281802 versus placebo on the change in hematology values over time (leucocytes, platelets and hematocrit) | 
 The maximal decrease from baseline (per participant) observed in platelet counts from Day 2 to Day 5 The maximal decrease from baseline (per participant) observed in leucocyte counts from Day 2 to Day 5 The maximal increase from baseline (per participant) observed in hematocrit concentration from Day 2 to Day 5 |
| 
 Investigate the effect of JNJ-64281802 versus placebo on the immunological profile | 
 The occurrence and magnitude of anti-DENV total IgM and IgG antibody titers |
| 
 To explore the effect of JNJ-64281802 versus placebo on DENV-related clinical signs and symptoms | 
 Time to resolution of dengue signs and symptoms Severity of dengue signs and symptoms |
| 
 To assess changes in the viral genome sequence (with a focus on NS4B) in participants with detectable DENV RNA | 
 Changes in the viral genome sequence at and between first viral isolation and last viral isolation |

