8.8. Immune Assessments

8.8.1. Humoral Immune Response

Blood samples will be obtained for the assessment of antibody response. Anti-DENV IgG and IgM will be measured using an in-house developed or commercial ELISA and the IgG pattern will be used to make a distinction between primary and secondary dengue infection. Presence of neutralizing antibodies against DENV will be determined using an assay such as flow cytometry-based neutralization assay.

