9.4.2.1. Primary Endpoint(s)

The difference in area under the log₁₀-transformed DENV RNA viral load curves from immediately prior to first dose (baseline) until Day 5 for JNJ-64281802 versus placebo dosing will be derived from a mixed model with treatment regimen and the stratification factors as fixed factors and baseline log₁₀ viral load as a covariate, calculating least square mean differences, including the 90% 2-sided confidence intervals in the ITT-I population with a primary dengue infection based on IgG profile.

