5.1.6. Demographics and Baseline Characteristics

Table 2 presents the list of demographic variables that will be reported in the patient profiles.

Table 2 – Demographic variables

Variables listed in patient profile
Age (years)
Weight at baseline (kg)
Height at baseline (cm)
BMI (kg/m ²)
Sex [Female; Male; Unknown; Undifferentiated]
Race ^a [American Indian or Alaska Native; Asian; Black or African American; Native Hawaiian or other Pacific Islander; White; Multiple; Not reported; Unknown]
Ethnicity [Hispanic or Latino; Not Hispanic or Latino; Not reported; Unknown]
Country

^a If multiple race categories are indicated, the Race is recorded as 'Multiple'.

Table 3 presents the list of baseline characteristics that will be reported in the patient profiles.

Table 3 – Baseline Characteristics

Variables listed in patient profile
Dengue NS1 rapid test result at screening/baseline [Positive; Negative; Equivocal]
Anti-Dengue IgG rapid test result at screening/baseline [Positive; Negative; Equivocal]
Anti-Dengue IgM rapid test result at screening/baseline [Positive; Negative; Equivocal]
Dengue RT-PCR test results at screening/baseline [Positive; Negative]
Duration of onset of fever until time of randomization (hours) [date/time of randomization – date/time of fever onset]
Does the subject have dengue hemorrhagic fever (DHF) at screening/baseline? [Yes; No] If yes, list symptoms
Does the subject have dengue shock syndrome (DSS) at screening/baseline? [Yes; No] If yes, list symptoms
What is the subject's childbearing potential? [Of Childbearing Potential; Permanently Sterilized; Postmenopausal; Premenarchal]
Does the subject have any history of Tobacco/Nicotine use? [Yes; No] If yes, Type of substance – Usage – Amount – Unit - Frequency

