Anti-DENV IgM antibody response (Panbio units)	A solid line is used for patients randomized to JNJ-64281802 and a dashed line is used for patients randomized to placebo. Different symbols and colors are used to distinguish each participant. Patient IDs together with DENV serotype will be shown. A horizontal line will be show at the negative (<9 Panbio units) and positive (>11 Panbio units) interpretation line.
Anti-DENV IgG [direct] antibody response (Panbio units) Anti-DENV IgG [indirect] antibody response (Panbio units)	A solid line is used for patients randomized to JNJ-64281802 and a dashed line is used for patients randomized to placebo. Different symbols and colors are used to distinguish each participant. Patient IDs together with DENV serotype will be shown. For direct IgG antibody response, a horizontal line will be show at the negative (<18 Panbio units) and positive (>22 Panbio units) interpretation line. For indirect IgG antibody response, a horizontal line will be show at the negative (<9 Panbio units) and positive (>11 Panbio units) interpretation line. Separate graphs are created for direct and indirect anti-DENV IgG antibody responses.
Barplot per patient	
Anti-DENV neutralizing antibody response (PRNT50)	The PRNT50 titer values will be shown in a barplot per patient by DENV serotype and visit (screening/baseline and Day 28). Treatment information and DENV infection serotype will be indicated in the plot.
Dengue Specific Signs and Symptoms	
DENV-Infection Associated Adverse Events	For each sign/symptom it is listed in the patient profile whether it occurred or not. If yes, report the date (study day) of first and last occurrence.

Per participant, an overlay graph will be created showing the following virological parameters over time: DENV RT-qPCR viral load; DENV NS1 serum protein levels; anti-DENV IgM antibody response; anti-DENV IgG [direct] antibody response; and anti-DENV IgG [indirect] antibody response. Treatment information will be indicated in the graph.

Combined graphs of virological variables and DENV-infection specific signs/symptoms (DENV-Infection Associated Adverse Events) could be created, if deemed useful.

DENV RT-qPCR viral load

Serum DENV RT-qPCR viral load will be assessed using a validated quantitative DENV RT - qPCR assay. Limits of detection (LOD) and lower limit of quantification (LLOQ) for each of the 4 serotypes on this assay are:

Serotype	DENV Parameter	LOD	LLOQ	Imputed values	
				LOD	LLOQ

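### Does selecting the primary-analysis subset by an IgG profile, with no stated limit to pre-dose samples, let treatment decide who enters the comparison?

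*Protocol*

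**What the plan says.** Protocol section 9.4.1 sorts participants before database lock into non-infected, primary and secondary groups, "based on all available virological information". It then adds: "The decision whether the participant had a primary or secondary infection will be based on the IgG profile". Section 8.8.1 names ELISA as the IgG method and says "the IgG pattern will be used to make a distinction between primary and secondary dengue infection". The primary analysis in section 9.4.2.1 is carried out "in the ITT-I population with a primary dengue infection based on IgG profile", adjusted for baseline log10 viral load and the stratification factors.

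The Schedule of Activities draws blood for IgG at screening and at several visits after dosing. Section 3 lists "The occurrence and magnitude of anti-DENV total IgM and IgG antibody titers" as an exploratory endpoint for drug versus placebo.

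Protocol sections 9 and 9.4 leave technical detail to the SAP. The released SAP has no rule for primary versus secondary status. It lists a baseline IgG rapid test (Table 3) and two IgG read-outs with different interpretation limits (Table 8): "Separate graphs are created for direct and indirect anti-DENV IgG antibody responses". SAP section 1 says that a stable draft existed and that outputs were cut back because only five participants were enrolled.

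**The concern.** Randomization protects a comparison in a subset only if membership does not depend on treatment. Here membership is settled late, from a marker measured serially, and the words profile and pattern read naturally as covering more than one sample. Both the interim and the primary analysis wait for Day 28, so post-dose IgG would be to hand.

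Infection class matters for the endpoint. Section 2.1 says viral load is higher and less variable in primary infection, and section 9.2 says RNA clears sooner in secondary infection. If the drug lowered or delayed IgG, some secondary cases on active drug could be read as primary, and their faster clearance would be credited to the drug. The opposite effect on IgG would remove some primary cases from the active arm. Blinding (section 6.3) restrains the assessor but cannot stop an affected sample from changing a participant's class. Infection class is not a stratification factor. The only planned hypothesis test could then rest on a biased contrast.

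**Working it through.** **The plan's own figure.** Section 9.2 gives 150 recruited, 60% primary, 2% lost to false-positive NS1 and 4% dropout. 150 × 0.60 × 0.98 × 0.96 = 84.7, which agrees with the stated 84. Per arm this is about 42.3 primary and 28.2 secondary, 141 evaluable in all.

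**Scale.** The SDs and correlations behind the power simulation are not given, so take the planned effect as 1 unit and power as exactly 80% at n = 80 (the plan says at least 80%). The noncentrality is 1.645 + 0.842 = 2.486. At n = 84 it is 2.486 × √(84/80) = 2.548, and power is Φ(2.548 − 1.645) = 81.7%.

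**Assumptions.** The documents give no misclassification rate and no AUC gap between classes. All values of q, g, p, d, m and h below are assumed. Gaps are taken as what remains after adjustment for baseline viral load.

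**Feared bias, case 1:** a fraction q of one arm's secondary cases is read as primary, with an AUC gap of g planned effects. Contamination c = 28.2q/(42.3 + 28.2q); shift f = c × g; power = Φ(2.548(1 ∓ f) − 1.645).

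| q | g | c | f | Power, shift against drug | Power, shift for drug |
|---|---|---|---|---|---|
| 0.10 | 0.5 | 0.0625 | 3.1% | 79.5% | 83.7% |
| 0.20 | 1.5 | 0.1176 | 17.6% | 67.5% | 91.2% |

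**Feared bias, case 2:** a fraction p of one arm's primary cases is read as secondary, and those moved differ from the rest by d planned effects. Shift = d × p/(1 − p). This is 0 if they are typical (d = 0), 5.6% for p = 0.10 and d = 0.5, and 25% for p = 0.20 and d = 1.0. In the last setting that arm falls to 42.3 × 0.8 = 33.8. The noncentrality before the shift is 2.486 × √[(2/40)/(1/42.3 + 1/33.8)] = 2.41, so power is Φ(2.41 × 0.75 − 1.645) = 56.5% or Φ(2.41 × 1.25 − 1.645) = 91.4%.

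**If the drug leaves IgG alone,** the shift is 0.

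**The alternative:** classify on pre-dose IgG only, with added error m in both classes and both arms. Then n = 84.7(1 − m) + 56.4m and c = 56.4m/n. The effect is 1 − c + c·h, with h the relative drug effect in secondary infection. SD = √(1.799² + c(1 − c)g²), where 1.799 = √80/(2 × 2.486). Power = Φ(effect × √n/(2·SD) − 1.645).

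| m | g | n | c | Power, h = 1 | Power, h = 0 |
|---|---|---|---|---|---|
| 0.10 | 0.5 | 82 | 0.069 | 80.6% | 75.5% |
| 0.20 | 1.5 | 79 | 0.143 | 76.7% | 65.1% |

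With h = 0 the estimate is also diluted by 7% to 14%. Simulated type I error under this rule stays at 4.8% to 5.1%.

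**Reading the text closely.** The phrase about virological information introduces the three-way sort, including infected versus not. The next sentence hands the primary/secondary split to IgG alone, and section 8.1 treats serologic and virologic characteristics as separate things. Section 8.8.1 makes ELISA the classifying assay, so the SAP's rapid test is not a rival candidate. What is really unwritten is the sampling time, the cut-off and the ELISA format.

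**The case for a change.** The strongest opposing case is that the two costs differ in kind. Equal misclassification in both arms leaves the test valid and pulls the estimate toward no effect. Treatment-dependent entry can push it either way. With no antiviral effect, and 10% to 30% of active-arm secondary cases read as primary with an AUC 0.25 to 1.0 residual SD lower, the nominal 5% one-sided error becomes about 5.8% to 19.3%. The same error in both arms (20%, 1.0 SD) gives a simulated 4.9%. A pre-dose sample is already scheduled, and which sample defines the primary population is arguably a matter for the protocol.

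The principle stands: a rule that treatment cannot touch is safer for validity, and the protocol would read better with the time point stated. The inflation figures carry less weight. They need a drug that changes IgG enough to reclassify participants yet leaves viral-load AUC unchanged, and nothing in the documents points to one. Listing IgG as an exploratory endpoint is not evidence of an effect. The accuracy of one sample taken within about two days of fever onset is equally undocumented, so the alternative also rests on an unknown.

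**Conclusion.** No change follows. The missing time point, cut-off and ELISA format are details the protocol left to the SAP. Their absence from the released SAP is explained by its reduction to patient profiles, and the full draft cannot be inspected. Classification before database lock, with provision in section 6.3 to segregate virologic and other laboratory data, already covers much of the procedural risk. Analysts applying an IgG-profile rule could be expected to tabulate class by arm and to check the result against a baseline-only classification.

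Replacing the profile by a pre-dose rule exchanges a possible shift of unknown direction for possible dilution. Under the assumed inputs, power after the shift spans 67.5% to 91.2% (case 1), or down to 56.5% in the most extreme form of case 2. Under the alternative it spans 65.1% to 80.6%. These ranges overlap, they are driven by assumed values, and they do not show that either rule is better. The shift is zero unless post-dose samples are used and the drug alters them enough to change class; the documents establish neither. SAP section 5.3 plans no efficacy testing in the five participants, so no reported result is affected.

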9.4.2. Antiviral Activity Analysis

The intent-to-treat infected (ITT-i) population will be used for all antiviral activity analyses. Treatment assignment for this population will be defined by actual treatment received.

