4.2. Scientific Rationale for Study Design

Blinding, Control, Study Phase/Periods, Intervention Groups

A placebo control will be used to establish the frequency and magnitude of changes in clinical endpoints that may occur in the absence of active intervention. Randomization will be used to minimize bias in the assignment of participants to intervention groups, to increase the likelihood that known and unknown participant attributes (eg, demographic and baseline characteristics) are

evenly balanced across intervention groups, and to enhance the validity of statistical comparisons across intervention groups. Blinded intervention will be used to reduce potential bias during data collection and evaluation of clinical endpoints.

DNA and Biomarker Collection

It is recognized that genetic variation can be an important contributory factor to interindividual differences in intervention distribution and response and can also serve as a marker for disease susceptibility and prognosis. Pharmacogenomic research may help to explain interindividual variability in clinical outcomes and may help to identify population subgroups that respond differently to an intervention. The goal of the pharmacogenomic component is to collect DNA to determine the human leukocyte antigen (HLA) type of each participant and to allow the identification of genetic factors that may influence the PK, antiviral activity, or safety/tolerability of JNJ-64281802. A blood sample for HLA genotyping and for pharmacogenomic research will be collected, preferably at baseline (ie, before first dose of study drug). Participation in the HLA genotyping and pharmacogenomic research is mandatory.

Biomarker samples will be collected to evaluate the mechanism of action of JNJ-64281802 or to help explain interindividual variability in clinical outcomes or may help to identify population subgroups that respond differently to an intervention. The goal of the biomarker analyses is to evaluate the impact of host and viral baseline factors on the antiviral activity and safety of JNJ-64281802 and aid in evaluating the drug-clinical response relationship. Samples can only be used for research related to JNJ-64281802 or DENV infection or may be used to develop tests/assays related to JNJ-64281802 or DENV infection.

DNA and Biomarker samples may be used to help address emerging issues and to enable the development of safer, more effective, and ultimately individualized therapies.

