6.4. Study Intervention Compliance

When participants are dosed at the site, they will receive study intervention directly from the investigator or designee, under medical supervision. JNJ-64281802 will be administered orally, by designated study-site personnel at the study sites, who will check the participant's mouth to confirm that the dose was swallowed. The date and time of each dose administered in the clinic will be recorded in the source documents and recorded in the CRF. The dose of study intervention and study participant identification will be confirmed at the time of dosing by a member of the study site personnel other than the person administering the study intervention.

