9.4.3. Safety Analyses

All participants enrolled into the study who received at least one dose of study intervention will be included in the safety population. Participants in this population will be defined by the study intervention actually received, not by randomization assignment. The safety population will be used for all safety analyses.

Safety data will be presented descriptively. No statistical testing of safety data is planned.

Adverse Events

The verbatim terms used in the CRF by investigators to identify adverse events will be coded using the Medical Dictionary for Regulatory Activities (MedDRA). Any AE occurring at or after the initial administration of study intervention through the day of last dose plus 20 days is considered to be treatment emergent. All reported adverse events will be included in the analysis. For each

adverse event, the percentage of participants who experience at least 1 occurrence of the given event will be summarized by intervention group.

Summaries, listings, datasets, or participant narratives may be provided, as appropriate, for those participants who die, who discontinue intervention due to an adverse event, or who experience a severe or a serious adverse event.

Clinical Laboratory Tests

Laboratory data will be summarized by type of laboratory test. Reference ranges and markedly abnormal results (specified in the Statistical Analysis Plan) will be used in the summary of laboratory data. Descriptive statistics will be calculated for each laboratory analyte at baseline and for observed values and changes from baseline at each scheduled time point. Changes from baseline results will be presented in pre- versus post-intervention cross-tabulations (with classes for below, within, and above normal ranges). Frequency tabulations of the laboratory abnormalities will be made. A listing of participants with any laboratory results outside the reference ranges will be provided. A listing of participants with any markedly abnormal laboratory results will also be provided.

Electrocardiogram

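### The primary superiority test uses an intent-to-treat population grouped by treatment actually received, and no as-randomised analysis is stated

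*Protocol*

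**What the plan says.** Protocol section 9.3 defines ITT-i as "All randomized participants with a DENV infection who received at least one dose of the study intervention". This fixes who is in the set but not how members are assigned to arms. Section 9.4.2 supplies both the use and the rule: "The intent-to-treat infected (ITT-i) population will be used for all antiviral activity analyses", and "Treatment assignment for this population will be defined by actual treatment received".

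The primary least-squares mean difference (section 9.4.2.1) is estimated in the ITT-i participants with primary infection. The test attached to it is in section 9.4.1: "A one-sided test at the 5% significance level will be used for the hypothesis that JNJ-64281802 is superior to placebo".

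The only other efficacy set, per-protocol, is a subset of ITT-i: "All participants who are included in the ITT-I population without protocol violations that affect the antiviral activity assessment". No separate grouping is given for it. The safety population in section 9.4.3 has the same rule as ITT-i; it is "defined by the study intervention actually received, not by randomization assignment".

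The final SAP (section 5.3) does no hypothesis testing because of the small enrolment. Its patient profiles list planned treatment (section 5.2) and actual treatment (section 5.1.7), and its spaghetti plots set line style by randomised arm.

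**The concern.** A randomised comparison is protected against confounding when participants are compared in the arms to which they were randomised. Grouping by treatment received gives up that protection for exactly the participants in whom the two groupings differ. The practice is usual for safety, but here it governs the one formal test of the trial.

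It also sits badly with the protocol's reason for randomising. Section 4.2 says "Randomization will be used to minimize bias in the assignment of participants to intervention groups" and adds that the validity of the statistical comparison is strengthened as a result.

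If receiving the wrong product is related to prognosis, as-treated grouping biases the primary estimate in either direction, and the true one-sided error can exceed the stated 5%. A reader who sees the intent-to-treat label would assume otherwise.

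**Working it through.** **Does any text restore an as-randomised analysis?** Section 9.3 names no grouping. Section 9.4.2 names actual treatment. Section 9.4.2.1 adds no sensitivity analysis by randomised arm. The SAP's line styles by randomised arm are a display, without an estimate or a test. The answer is no.

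**The plan's own sample size.** Inputs from protocol section 9.2: 150 recruited, 2% not evaluable, 4% dropout, 60% primary infection.

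150 × 0.98 × 0.96 × 0.60 = 84.7, against 84 stated. This reproduces and gives 42 per arm. The stated power of at least 80% at 40 per arm comes from a simulation whose SDs and correlations are not given, so it cannot be re-derived. I take 80% as given and solve for the effect it implies.

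**Calibration.** Set the residual SD to 1. With a noncentral t, one covariate degree of freedom, one-sided 5% and 40 per arm, 80% power implies an effect d = 0.561 SD. At 42 per arm the power is 81.7%.

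**Assumptions not in the documents.** Let k placebo-randomised participants receive active drug, with a prognosis D residual SDs better than the placebo-arm average, the arm mean being unchanged. Assume no drug effect.

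**Bias under as-treated grouping.** Removing these k from placebo worsens that arm's mean by Dk/(42 − k). Adding them to the active arm improves its mean by Dk/(42 + k). So

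bias = Dk/(42 − k) + Dk/(42 + k).

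For k = 1, D = 1: 1/41 + 1/43 = 0.048 SD, and 0.048/0.561 = 8.5% of the design effect. For D = 0.5 the bias is 0.024 SD, or 4.2%.

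**One-sided error, as-treated (nominal 5%):**

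| k | D = +0.5 | D = +1 | D = −0.5 | D = −1 |
|---|---|---|---|---|
| 1 | 6.2% | 7.7% | 4.0% | 3.1% |
| 2 | 7.7% | 11.3% | 3.1% | 1.9% |

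Simulation with 200,000 trials per case, k = 1 and D = 1, gives 7.5% as-treated and 4.9% as-randomised. With one error in each direction and the same prognosis shift, the biases cancel and both groupings give 4.7%.

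**Power when errors are unrelated to prognosis (42 per arm).** As-randomised grouping dilutes the effect to d(1 − k/42) for k one-way cases and d(1 − 2k/42) for k per arm.

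| Wrong-treatment cases | As-randomised power |
|---|---|
| none | 81.7% |
| 1 in total | 80.1% |
| 2 in total, same direction | 78.3% |
| 1 per arm | 78.3% |
| 2 per arm | 74.6% |

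As-treated power in the same cases stays at 81.6% to 81.7%.

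**The case against.** The strongest reply is that the harm has no stated mechanism. The two groupings agree unless someone receives the other arm's product. The trial is double-blind with identical products, site staff give each dose, and the dose and participant identity are confirmed "by a member of the study site personnel other than the person administering the study intervention". A dispensing slip under those conditions would normally be unrelated to prognosis, all the more so after adjustment for baseline viral load and the stratification factors. In that case as-treated grouping is unbiased and keeps slightly more power. The inflated error rates come from fixing a one-directional shift in one or two people; the opposite sign lowers the error.

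It can also be said that the trial stopped with five participants, so no reported estimate depends on the rule. Further, section 9.4 is a summary, and a draft SAP that predates termination is mentioned in the SAP introduction but is not available. It may have contained an as-randomised analysis.

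Much of this stands. Errors should be rare, the inflated figures are conditional illustrations, and nothing reported changes. It bears on size, not on whether the rule is wrong. Section 9.4.2 states the rule outright, so an unseen draft cannot be assumed to reverse it. Rarity also makes the correction nearly free: without errors the groupings coincide, and with errors only the as-randomised grouping holds the 5% level without assuming that the errors are unrelated to prognosis.

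**Conclusion.** The concern holds. The protocol's primary superiority test is as-treated under an intent-to-treat label, and neither document states an as-randomised analysis.

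The size is small: zero without wrong-product dosing. Under the assumed single one-way case with a shift of 0.5 to 1 SD, the one-sided error moves to between 3.1% and 7.7%, depending on the sign; with two such cases, to between 1.9% and 11.3%. These ranges rest on assumed values of k and D and on an effect calibrated to the plan's 80% power. The defect lies in the planned protocol analysis; the final SAP makes no test that it could affect. It should be corrected in the protocol text and in any later protocol that reuses it.

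**What to change.** Replace the grouping sentence in protocol section 9.4.2 with:

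> Participants in the ITT-i population will be analysed according to the treatment group to which they were randomised.

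Keep actual treatment for the safety and PK sets and, if wanted, for an as-treated sensitivity analysis of the primary endpoint.

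The cost is one sentence. The recruitment target, evaluable number and significance level do not change. The downside is the loss of power shown above if dosing errors unrelated to prognosis occur: 1.6 points for one case in total (81.7% to 80.1%) and 3.4 points for one per arm (81.7% to 78.3%). There is no loss if there are no errors.
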